14.0 DATA MANAGEMENT

14.1 Electronic Case Report Form (e-CRF)

Data will be collected for each patient by an e-CRF located on a website. The e-CRF will allow the collection of the main demographic and clinical data including the patient's medical history and concomitant therapies. All data must accurately reflect the patients' view, or be an expression of their knowledge about their health.

The following data will be entered in the e-CRF, for each subject and visit:

- Age
- Gender
- Height
- Weight
- Ethnicity
- Superficial distance between jugulum and symphysis (surrogate of aortic length)
- Waist circumference
- Smoking status
- Alcohol drinking
- Coffee or tea drinking
- Dyslipidemia (yes/no and indication on treatment)
- Diabetes (yes/no and indication on treatment)
- Diagnosis of hypertension (yes/no and indication on treatment)
- Family history of premature CV disease
- Medical history, with particular regard to previous and/or concurrent CV diseases
- Office blood pressure and heart rate obtained in the same treatment condition as ABPM
- Left ventricular mass index (LVMI) at echocardiogram
- When available, diameter of the aorta (aortic annulus, root and sinotubular junction) and/or cardiac output, assessed by the echocardiogram
- Intima-media thickness (IMT) at carotid ultrasonography
- ECG (indication on left ventricular hypertrophy, Sokolow–Lyon and Cornell index)
- When available, ankle-brachial index

- Microalbuminuria and serum creatinine (calculation of estimated glomerular filtration rate - eGFR)
- When available, pulse wave velocity (PWV) augmentation index (AI) and central blood pressure taken during the office visit with a validated device different for BPLab Vasotens (e.g. Sphygmocor or Complior)

Access to the e-CRF will be granted through authentication with ID and password. The investigator will be responsible for the faithful transcription of the results of any laboratory or instrumental diagnostic tests. If changes have to be made to data, they will be overwritten with the correct ones. The system will keep record of the date and time of the corrections.

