### 2.2 CLINICAL DATA

That CRF must be completed with all the following information:

- Age
- Gender
- Height

- Weight
- Ethnicity
- Superficial distance between jugulum and symphysis (surrogate of aortic length) – see above
- Waist circumference
- Smoking status
- Alcohol drinking
- Coffee or tea drinking
- Dyslipidemia (yes/no and indication on treatment)
- Diabetes (yes/no and indication on treatment)
- Diagnosis of hypertension (yes/no and indication on treatment)
- Family history of premature CV disease
- Medical history, with particular regard to previous and/or concurrent CV diseases
- Office blood pressure and heart rate obtained in the same treatment condition as ABPM (only one value can be input: it could be the average of more values or just a spot measurement)
- Left ventricular mass index (LVMI) at echocardiogram
- When available, diameter of the ascending aorta assessed by the echocardiogram
- Intima-media thickness (IMT) at carotid ultrasonography
- ECG (indication on left ventricular hypertrophy, Sokolow–Lyon and Cornell index)
- When available, ankle-brachial index
- Microalbuminuria (as mg/24h) or albumin-creatinine ratio (as mg/g) and serum creatinine (estimated glomerular filtration rate – eGFR will be calculated by the software according to the Cockcroft-Gault formula)
- When available, pulse wave velocity (PWV), augmentation index (AI) and central systolic blood pressure taken during the office visit with a validated device different from BPLab Vasotens (e.g. Sphygmocor or Complior)

Additionally, this information must be recorded at any visit:

- Drug treatments: explain that in case treatments are changed or replaced the Investigator must indicate dates and status. It is not necessary to add the drug again.
- Investigators must pay attention to record at any visit both new diseases and adverse events: the latter must be recorded in the “Events” section with start and end date and all the information needed to identify the event. Priority must be given to cardiovascular events, whereas other events must be placed under the label “Other” and a description must be entered.

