### 3.2 EVALUATION OF TARGET ORGAN DAMAGE

#### 3.2.1 CARDIAC DAMAGE

Cardiac damage will be based on LVMI, calculated as LVM divided by BSA, as follows [Devereux RB, Alonso DR, Lutas EM, Gottlieb GJ, Campo E, Sachs I, Reichel N. Echocardiographic assessment of left ventricular hypertrophy: comparison to necropsy findings. Am J Cardiol 1986;57:450-458]:

$$LVM = ( (1.04 * ( ( (IVSD + PWD + LVEDD)^3) / 1000 ) - ( (LVEDD^3) / 1000 ) ) - 3.6 ) / ( (WEIGHT^{0.425}) * (HEIGHT^{0.725}) * 0.007184 ) )$$

Where:

IVSD = Interventricular septal thickness at end-diastole (mm)

PWD = Posterior wall thickness at end-diastole (mm)

LVEDD = LV end-diastolic dimension (mm)

Height is expressed in cm and weight in kg.

LVMI will be recalculated from LVM.

Cardiac damage will be assessed according to ESH guidelines [Mancia G, Fagard R, Narkiewicz K, Redón J, Zanchetti A, Böhm M, Christiaens T, Cifkova R, De Backer G, Dominiczak A, Galderisi M, Grobbee DE, Jaarsma T, Kirchhof P, Kjeldsen SE, Laurent S, Manolis AJ, Nilsson PM, Ruilope LM, Schmieder RE, Sirnes PA, Sleight P, Viigimaa M, Waeber B, Zannad F; Task Force Members. 2013 ESH/ESC Guidelines for the management of arterial hypertension: the Task Force for the management of arterial hypertension of the European Society of Hypertension (ESH) and of the European Society of Cardiology (ESC). J Hypertens. 2013 Jul;31(7):1281-357]:

- Males: LVMI > 115 g/m^2
- Females: LVMI > 95 g/m^2

An attempt will also be made to classify left ventricular hypertrophy according to ECG:

- Sokolow-Lyons index: SV1+RV5-6 >38 mm
- Cornell Index; S in V3 + R in aVL >24 mV in males and > 20 mV in females

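### SAP 3.2.1: the line labelled LVM is already divided by body surface area, yet LVMI is then derived from it, and the Cornell cut-offs are in mV beside a Sokolow-Lyon cut-off in mm

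*SAP*

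**What the plan says.** SAP 3.2.1 (Cardiac damage) opens with the definition: "Cardiac damage will be based on LVMI, calculated as LVM divided by BSA, as follows". The formula below it is labelled LVM. Its numerator is a mass computed from septal thickness (IVSD), posterior wall thickness (PWD) and end-diastolic dimension (LVEDD). Its denominator is "WEIGHT^{0.425}) * (HEIGHT^{0.725}) * 0.007184", with height in cm and weight in kg, which is the only BSA expression in the section. The next instruction is "LVMI will be recalculated from LVM". The result is compared with sex-specific limits: "Males: LVMI > 115 g/m 2", and 95 g/m² for females.

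For the supplementary ECG classification the same section gives "Sokolow-Lyons index: SV1+RV5-6 >38 mm" and then "Cornell Index; S in V3 + R in aVL >24 mV in males and > 20 mV in females".

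Neither point is settled elsewhere. SAP 2.2 lists "Left ventricular mass index (LVMI) at echocardiogram" as a field completed by the site, without a formula. Protocol 14.1 lists "ECG (indication on left ventricular hypertrophy, Sokolow–Lyon and Cornell index" without a unit, and SAP 2.2 does the same.

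**The concern.** Three statements in SAP 3.2.1 cannot all stand: that LVMI is LVM over BSA, that LVM is the line shown (already over BSA), and that LVMI is then obtained from that LVM. A programmer who follows the label and the recalculation sentence divides by BSA twice. The result is in g/m⁴ and is judged against limits in g/m².

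SAP 3 places target organ damage in the main analysis, and cardiac damage rests on LVMI. The literal error runs in one direction: it hides damage, and more so in larger patients, because the acting cut-off rises with BSA. That could distort the relation between arterial stiffness and organ damage that the registry sets out to study.

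The ECG lines have a separate fault. Both indices are sums of ECG wave amplitudes, but one limit is in mm and the other in mV, and the two are not on a comparable scale. SAP 3.1 also recodes missing ECG hypertrophy to 0, so a Cornell limb that is almost never met would add zeros that look the same as recoded missing values.

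**Working it through.** The documents give no worked LVMI value to reproduce. The formula was therefore evaluated for assumed patients, dividing by BSA once and then twice.

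**Inputs from SAP 3.2.1**
- BSA = weight^0.425 × height^0.725 × 0.007184
- Numerator as printed: P = 1.04 × (IVSD + PWD + LVEDD)³/1000 − LVEDD³/1000 − 3.6
- Cut-offs: 115 g/m² (men) and 95 g/m² (women)

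Patient dimensions, weights and heights are assumptions.

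**Step 1: how the cut-off shifts.** P/BSA² > c is the same condition as P/BSA > c × BSA.
- Men: 115 × 1.6 = 184 and 115 × 2.2 = 253 g/m²
- Women: 95 × 1.6 = 152 and 95 × 2.2 = 209 g/m²

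**Step 2: one example in full.** Man, 13/13/52 mm (IVSD/PWD/LVEDD), 85 kg, 175 cm, BSA 2.007. P = 1.04 × 78³/1000 − 52³/1000 − 3.6 = 493.5 − 140.6 − 3.6 = 349.3 g. One division gives 174.0, which is above 115. Two divisions give 86.7, which is below.

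**Step 3: six assumed patients**

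| Sex | IVSD/PWD/LVEDD (mm) | kg, cm | BSA | P/BSA | P/BSA² | Class |
|---|---|---|---|---|---|---|
| M | 10/10/48 | 82, 175 | 1.977 | 107.7 | 54.5 | not damaged either way |
| M | 13/13/52 | 85, 175 | 2.007 | 174.0 | 86.7 | changes |
| M | 15/15/56 | 85, 175 | 2.007 | 240.3 | 119.7 | damaged either way |
| F | 9/9/46 | 68, 163 | 1.734 | 99.0 | 57.1 | changes |
| F | 12/12/48 | 70, 163 | 1.755 | 156.1 | 88.9 | changes |
| F | 14/14/52 | 70, 163 | 1.755 | 221.2 | 126.0 | damaged either way |

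**Step 4: wall thickness needed to exceed the cut-off**, with IVSD = PWD
- Man, LVEDD 50 mm, 85 kg, 175 cm: 10.1 mm with one division, 16.4 mm with two. From 65 kg/165 cm to 100 kg/180 cm: 9.0 to 10.8 mm against 13.3 to 18.5 mm.
- Woman, LVEDD 46 mm, 70 kg, 163 cm: 8.8 mm with one division, 13.2 mm with two. From 58 kg/155 cm to 90 kg/170 cm: 8.1 to 9.7 mm against 11.2 to 15.8 mm.

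**Step 5: ECG units.** The documents give no calibration. At an assumed 10 mm per mV, 24 and 20 mV are 240 and 200 mm; 240/38 = 6.3 and 200/38 = 5.3. Over an assumed 5 to 20 mm per mV the ranges are 120 to 480 mm and 100 to 400 mm; the smallest ratio is 100/38 = 2.6.

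**Step 6: brackets (minor).** The formula as read from the PDF has 10 opening and 11 closing brackets, and 1.04 multiplies only the outer cube. Applying 1.04 to the difference of the cubes lowers the mass by 0.04 × LVEDD³/1000 g. That is 2.56 g at 40 mm (÷ 2.2 = 1.2 g/m²) and 8.64 g at 60 mm (÷ 1.6 = 5.4 g/m²). No class in the table changes. Near a cut-off one can: an assumed man of 10/10/50 mm, 80 kg, 175 cm has 116.6 as printed and 114.1 with 1.04 over both cubes.

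**The case against.** The strongest reply is that the section can be read coherently with a single division. The lead sentence announces LVMI, what follows is mass over BSA, and only one division fits g/m². On that reading a letter is missing from a label, and no result changes. Nothing in the documents shows code that divides twice, and the patient examples illustrate the less likely reading. This all stands, and it limits the point to a coding risk. It does not remove it: the label and the recalculation sentence still instruct otherwise, and a derivation rule should not require the programmer to guess.

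On the ECG, the rule is explicitly supplementary, the e-CRF also records an indication of hypertrophy apart from the indices, and the two indices use different leads, so the ratio to 38 mm gives scale and does not measure an error. That also stands, but the unit mismatch remains.

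On the brackets, restoring one opening bracket after 1.04 would balance the formula and put 1.04 over both cubes. A character lost in conversion is therefore a plausible explanation, and the item is only something to check.

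On cost, the listed clinical data name LVMI but not IVSD, PWD or LVEDD. The SAP formula already requires those three measurements, however, so correcting it adds no data need.

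**Conclusion.** The concern holds. SAP 3.2.1 is wrong as written on two counts: the LVM line, its denominator and the recalculation sentence are mutually inconsistent, and the Cornell and Sokolow-Lyon limits are in units that do not fit together.

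The size is conditional. If the line is read as LVMI, correcting the label leaves every classification unchanged. If the text is followed literally, the cut-offs are inflated by a factor equal to BSA, and three of the six assumed patients move from damaged to not damaged. That count illustrates the effect and does not estimate it for the registry. The ECG figures rest on an assumed calibration and affect only a supplementary rule. This should be fixed before analysis.

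**What to change.** - Either relabel the line as LVMI and state that the recalculation means central recomputation of the site-entered value, or print LVM (in g) as the numerator alone, followed by LVMI = LVM/BSA, applied once.
- Check the Sokolow-Lyon and Cornell cut-offs against their source, express both in one stated unit, and name that unit for the e-CRF fields.
- Confirm in the analysis code that BSA enters once and that the ECG values and limits share a unit.
- Compare the brackets of the formula with the original document.

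The cost is a few lines of SAP wording and a code check. No data are needed beyond what the SAP formula already requires.

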#### 3.2.2 VASCULAR DAMAGE

Carotid damage will be defined as thickening or plaque: Intima Media Thickness (IMT) in any district >0.9 mm. If available also an ankle-brachial index (ABI) <0.9 will be used for classification

#### 3.2.3 RENAL DAMAGE

Renal damage will be defined according to:

- Estimated Glomerular Filtration Rate (GFR): <60 mL/min/1.73 m^2
- Urinary Albumin creatinine (UAC) ratio: ≥30 mg/g
- Microalbuminuria: ≥30 mg/24 hour

eGFR will be calculated according to the Cockcroft-Gault formula [Cockcroft DW, Gault MH. Prediction of creatinine clearance from serum creatinine. Nephron 1976;16:31-41]

- Male =  $[(140 - \text{age}) * (\text{weight}) * 1] / (72 * \text{creatinine})$
- Female =  $[(140 - \text{age}) * (\text{weight}) * 0,85] / (72 * \text{creatinine})$

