### 3. ANALYSIS

The main analysis will assess:

- The general clinical characteristics of the population
- The relationship between BP and arterial stiffness and target organ damage / cardiovascular events
- The features of BP and arterial stiffness in presence of the metabolic syndrome

The following inclusion criteria will be considered:

- Male and female aged  $\geq 18$  years
- Good quality ABPM: i) at least 70% of the number of the expected readings over the 24 hours (discarded), ii) at least 20 valid measurements during the daytime and 7 during the nighttime

The parameters assessed will be:

- 24-hour average brachial SBP and DBP
- 24-hour average aortic SBP and DBP
- 24-hour average PWV
- 24-hour average aortic AI

- 24-hour wSD of SBP and DBP
- 24-hour ARV of SBP and DBP

Analysis will be done also for the day-time and night-time subperiods.

In each individual PWV will be normalized to a SBP of 100 mmHg and a HR of 60 bpm by a regression analysis of 24-hour PWV to 24-hour SBP and 24-hour HR. AI will be normalized to a HR of 75 bpm with the same procedure.

Statistical tests to be used will include analysis of variance (ANOVA) or covariance (ANCOVA) for continuous variables with adjustments for confounding factors. Discrete variables will be analyzed by Chi-square test or logistic regression analysis. Survival analysis will be carried out by Kaplan-Meier plots, log rank test and Cox regression.

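### The eGFR criterion for renal damage compares an unindexed Cockcroft-Gault clearance (mL/min) with a cut-off per 1.73 m², so it misses damage in larger patients and falsely flags it in smaller ones

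*SAP*

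**What the plan says.** SAP 3.2.3 lists three criteria for renal damage: an eGFR criterion, a urinary albumin-creatinine ratio and a 24-hour microalbuminuria value. The eGFR criterion is "Estimated Glomerular Filtration Rate (GFR): <60 mL/min/1.73 m"², that is, a rate per 1.73 m² of body surface. The same section then says "eGFR will be calculated according to the Cockcroft-Gault formula" and prints the formula in full for each sex: (140 − age) × weight / (72 × creatinine), with a factor of 0.85 for women.

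SAP 2.2 repeats the choice of estimator for the data-capture system: "eGFR will be calculated by the software according to the Cockcroft-Gault formula". Protocol 14.1 lists only "Microalbuminuria and serum creatinine (calculation of estimated glomerular filtration rate - eGFR") and names no equation.

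The SAP does index by body size elsewhere. For the heart, SAP 3.2.1 says "Cardiac damage will be based on LVMI, calculated as LVM divided by BSA, as follows", and the BSA expression is printed there.

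**The concern.** The value computed and the threshold applied are in different units. The printed formula has no height, no BSA and no factor of 1.73, so it gives a clearance in mL/min. The threshold is per 1.73 m². Because the formula is written out completely, a programmer who follows the SAP will compare one directly with the other.

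The resulting error is systematic in body size. It runs in one direction above 1.73 m² and in the other below.

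This matters because SAP 3 lists among its main analyses "The relationship between BP and arterial stiffness and target organ damage / cardiovascular events", and the eGFR criterion is part of how renal damage enters that analysis. SAP 3 plans adjustment for confounders but names none, so adjustment for body size is not assured.

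**Working it through.** The plan states no figure on this point, so there is nothing to reproduce. The check is one of units followed by direct arithmetic.

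**Inputs**
- Threshold: 60 mL/min/1.73 m² (SAP 3.2.3).
- CG = (140 − age) × weight × k / (72 × creatinine), with k = 1 for men and 0.85 for women (SAP 3.2.3).
- BSA = weight^0.425 × height^0.725 × 0.007184, in kg and cm (SAP 3.2.1).
- Assumed: creatinine in mg/dL, because the SAP gives no unit. The patients below are illustrative.

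**Effective cut-off.** Indexed CG = CG × 1.73/BSA. Flagging when unindexed CG < 60 is therefore the same as flagging when indexed CG < 60 × 1.73/BSA.

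| Weight, height | BSA (m²) | Effective indexed cut-off |
|---|---|---|
| 100 kg, 175 cm | 2.15 | 48.3 |
| 80 kg, 175 cm | 1.96 | 53.1 |
| 70 kg, 170 cm | 1.81 | 57.4 |
| 65 kg, 165 cm | 1.72 | 60.5 |
| 50 kg, 155 cm | 1.47 | 70.8 |

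**Where the error changes sign.** Setting BSA = 1.73 gives weight = (1.73 / (height^0.725 × 0.007184))^(1/0.425). This is 59.9 kg at 175 cm, 66.2 kg at 165 cm and 73.7 kg at 155 cm.

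**Who changes class.** Only patients whose unindexed CG lies between 60 and 60 × BSA/1.73 mL/min. At BSA 2.0 the band is 60 to 69.4 (missed). At BSA 1.5 it is 52.0 to 60 (falsely flagged).

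**Man, 62 years, 105 kg, 175 cm; BSA 2.196**
- As written, flagged when creatinine > 78 × 105 / (72 × 60) = 1.896.
- Indexed, flagged when creatinine > 1.896 × 1.73/2.196 = 1.494.
- To two decimals, every creatinine from 1.50 to 1.89 is missed. At 1.6, CG is 71.1 as written and 56.0 indexed.

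**Woman, 65 years, 50 kg, 155 cm; BSA 1.467**
- As written, flagged when creatinine > 75 × 50 × 0.85 / (72 × 60) = 0.738.
- Indexed, flagged when creatinine > 0.738 × 1.73/1.467 = 0.870.
- To two decimals, every creatinine from 0.74 to 0.87 is falsely flagged. At 0.75, CG is 59.0 as written and 69.6 indexed.

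**What indexing leaves behind.** CG is proportional to weight and BSA to weight^0.425, so indexed CG is proportional to weight^0.575. At equal age, height and creatinine, 100 kg against 70 kg reads 100/70 = 1.43 times as high as written, and (100/70)^0.575 = 1.23 times as high after indexing.

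**The case against.** The mismatch itself is hard to dispute. The case on the other side concerns its reach and its remedy.

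- **Reach.** Not every patient above or below 1.73 m² is affected, only those in the band given above. Near the crossover the band is narrow: for a man of 62 years, 70 kg and 170 cm, only creatinine from about 1.21 to 1.26 mg/dL changes class. The two worked patients are well away from the crossover. This stands as a limit on size. The 80 kg, 175 cm row, with a cut-off of 53.1, shows that the effect is not confined to extreme builds.
- **Reference standard.** Calling a patient missed or falsely flagged treats indexed Cockcroft-Gault as the yardstick, and that quantity still varies with weight. This is fair as far as true renal function goes: the documents contain no measured GFR. But the yardstick here is the threshold the SAP itself sets, and against that the labels are correct.
- **Other repairs.** Restating the cut-off in mL/min would also reconcile the units, and the documents do not show which half was intended. That would drop the indexed threshold the SAP now states and leave the full dependence on weight in place.
- **Consequence.** eGFR is one of three renal criteria, and renal damage sits beside cardiac and vascular damage. A patient missed on eGFR may still qualify through albuminuria. That does not help a patient who is falsely flagged if any one criterion suffices, and the SAP does not say how the three combine. All inputs are stored, so the error is reversible. These points argue against a higher grade, not against correction.

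**Conclusion.** The concern holds. As written, the SAP misapplies its own renal threshold: the effective indexed cut-off is 60 × 1.73/BSA, which runs from 48.3 to 70.8 across the body sizes tabulated, instead of a constant 60. The cut-offs do not depend on the creatinine unit; the two worked patients assume mg/dL.

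The share of patients misclassified is unknown, because the documents give no distribution of weight, BSA or creatinine. For the same reason, the direction and size of any bias in the association of BP or arterial stiffness with organ damage cannot be derived. The two albuminuria criteria are unaffected, and no stated metabolic-syndrome comparison uses renal damage. This should be fixed before analysis.

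**What to change.** Recompute eGFR centrally before analysis from age, sex, weight, height and creatinine, instead of taking the value from the data-capture software. SAP 3.2.3 should adopt one of two routes, and SAP 2.2 should be made to agree:

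1. Use a creatinine equation that returns mL/min/1.73 m² directly.
2. Keep Cockcroft-Gault and multiply by 1.73/BSA, using the BSA expression already in SAP 3.2.1.

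If the second route is chosen, state that a dependence of about weight^0.575 remains (23% for 100 kg against 70 kg) and name body size among the adjustment factors. Under either route, state the creatinine unit, since the constant 72 depends on it.

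The cost is one or two lines of SAP text and code. No new data are needed: Protocol 14.1 already has every input entered for each subject and visit.

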### 3.2 EVALUATION OF THE METABOLIC SYNDROME

The metabolic syndrome will be evaluated according to the harmonized definition [Alberti KG, Eckel RH, Grundy SM, Zimmet PZ, Cleeman JI, Donato KA, Fruchart JC, James WP, Loria CM, Smith SC Jr; International Diabetes Federation Task Force on Epidemiology and Prevention; National Heart, Lung, and Blood Institute; American Heart Association; World Heart Federation; International Atherosclerosis Society; International Association for the Study of Obesity. Harmonizing the metabolic syndrome: a joint interim statement of the International Diabetes Federation Task Force on Epidemiology and Prevention; National Heart, Lung, and Blood Institute; American Heart Association; World Heart Federation; International Atherosclerosis Society; and International Association for the Study of Obesity. Circulation. 2009 Oct 20;120(16):1640-5]. Presence of 3 out of 5 of the following risk factors

a) Elevated waist circumference (Caucasian)

≥94 cm in males  
≥80 cm in females

Elevated waist circumference (South America and Asia)

≥90 cm in males  
≥80 cm in females

When waist circumference is missing a BMI  $\geq 25 \text{ kg/m}^2$  will be used

- b) Elevated triglycerides ( $\geq 150 \text{ mg/dL}$ ) or lipid-lowering treatment
- c) Reduced HDL cholesterol ( $< 40 \text{ mg/dL}$  males and  $< 50 \text{ mg/dL}$  females) or lipid-lowering treatment
- d) Elevated blood pressure ( $\geq 130 / 80 \text{ mmHg}$ ) or antihypertensive treatment
- e) Elevated fasting glucose ( $\geq 100 \text{ mg/dL}$ ) or treatment for diabetes

In case of missing HDL it will be calculated in presence of total cholesterol, LDL cholesterol and triglycerides as

$$\text{HDL} = \text{Total cholesterol} - \text{LDL cholesterol} - \text{Triglycerides} / 5$$

Also Cholesterol LDL and Triglycerides, if missing, will be recalculated starting from the available parameters.

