### 3.1 EVALUATION OF CLINICAL CHARACTERISTICS

Evaluation and comparison of the main study parameters for the following groups:

- Males vs. females
- Young (<65 years) vs. old ( $\geq 65$  years)
- Age at risk:  $\geq 55$  years in males and age  $\geq 65$  years in females
- Ethnicity
- Smoking (smoker, no smoker, ex-smoker)
- Alcohol (yes vs. no)
- Coffee or tea (yes vs. no)
- Smoking or alcohol or coffee (yes vs. no)
- Family history for cardiovascular disease (yes vs. no)
- Previous cardiovascular diseases (yes vs. no)
- Any previous medical condition (yes vs. no)
- Arterial hypertension (untreated and treated)
- Antihypertensive treatment (yes vs. no)
- Dyslipidemia (untreated and treated)
- Lipid lowering treatment (yes vs. no)
- Diabetes (untreated and treated)
- Treatment of diabetes (yes vs. no)
- Metabolic syndrome (yes vs. no)
- Any cardiovascular disease (TIA, stroke, myocardial infarction, etc.) (yes vs. no)

Race will be modified according to the following rule in order to calculate ethnicity (missing values will be recoded into an appropriate value and if no category can be identified the “Caucasian” group will be assigned)

- Caucasian (1)
- Black (2)
- Asian (3)
- Hispanic (4)

In case of missing value for the following variables the missing value will be recoded to 0:

- Smoking
- Alcohol
- Coffee
- Left ventricular Hypertrophy at the ECG
- Family history for any CV disease
- Hypertension and therapy
- Number of antihypertensive drugs
- Dyslipidemia and therapy

- Diabetes and therapy
- Concomitant diseases and treatments
- Cardiovascular disease
- Cardiovascular risk
- Component of the metabolic syndrome and metabolic syndrome

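### The metabolic syndrome definition has no fallback for missing fasting glucose, so a recorded but untreated diabetic with a blank glucose value is scored as not meeting the glucose component

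*SAP*

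**What the plan says.** SAP 3.2 (Evaluation of the metabolic syndrome) defines the syndrome as "Presence of 3 out of 5 of the following risk factors". Component e is "Elevated fasting glucose", with a cut-off of 100 mg/dL, "or treatment for diabetes". No other route to the component is given.

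The same section handles some missing inputs. BMI replaces a missing waist measurement, and HDL, LDL and triglycerides are back-calculated from the other lipid values where possible. It says nothing about missing glucose.

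SAP 3.1 (Evaluation of clinical characteristics) adds a general rule: "In case of missing value for the following variables the missing value will be recoded to 0". Its list includes "Component of the metabolic syndrome and metabolic syndrome" and "Diabetes and therapy".

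Diabetes status is recorded separately from its treatment: SAP 2.2 collects "Diabetes (yes/no and indication on treatment", as does Protocol 14.1. SAP 3.1 names "Diabetes (untreated and treated" as a grouping, so the plan expects some diabetic patients to be untreated and can identify them.

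**The concern.** Taken together, the rules in SAP 3.1 and 3.2 turn an absent laboratory value into a negative finding for a patient whose record already says diabetes. The untreated diabetic with a blank glucose field gets the same component score as a non-diabetic with a blank glucose field, and the recorded diagnosis is not used.

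Blank glucose values are plausible. Neither SAP 2.2 nor Protocol 14.1 names fasting glucose among the data items; Protocol 10.1 refers only to laboratory tests in general. Much of the registry may also come from existing databases (Protocol 9.0), where a missing value may not be recoverable.

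SAP 3 makes BP and arterial stiffness in the metabolic syndrome one of three main analysis topics. An error that only ever moves patients from the syndrome group to the comparison group will, if the moved patients resemble the syndrome group, shrink the difference between the two.

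**Working it through.** The plan states no figure on this point, so there is nothing to reproduce. The check applies the rules as written and then sizes the effect.

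**Step 1. Component e as written, with missing recoded to 0**

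| Diabetes record | Glucose missing | Glucose 95 mg/dL | Glucose 110 mg/dL |
|---|---|---|---|
| None | 0 | 0 | 1 |
| Yes, untreated | **0** | 0 | 1 |
| Yes, treated | 1 | 1 | 1 |

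The cell in bold is the problem. A patient recorded as diabetic with therapy blank falls into the same row, because SAP 3.1 also recodes missing diabetes therapy to 0.

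**Step 2. When the syndrome label changes**

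The label needs 3 of 5 components, so component e decides it only when exactly 2 of the other 4 are met.

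- All patterns of the other four: C(4,2) = 6 of 2^4 = 16.
- Blood pressure component already met: exactly 1 of the remaining 3, so 3 of 2^3 = 8.

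These are counts of patterns, not expected shares of patients.

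**Step 3. Worked case**

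A Caucasian man has a waist of 98 cm (at least 94, so a = 1), is on antihypertensive treatment (d = 1), meets neither lipid component (b = c = 0), and has diabetes recorded as untreated with glucose blank (e = 0). Total: 1 + 0 + 0 + 1 + 0 = 2, so no syndrome. If the recorded diagnosis filled the gap, e = 1 and the total would be 3, so syndrome present.

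**Step 4. Size**

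The base is 30 centers × 100 patients = 3,000, the minimum in the Protocol synopsis. The four rates below are assumptions; none is in the documents.

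| Input | Low | Middle | High |
|---|---|---|---|
| Diabetes | 10% | 15% | 20% |
| Untreated, of diabetics | 10% | 15% | 25% |
| Glucose missing | 25% | 50% | 100% |
| Exactly two other components met | 30% | 40% | 50% |

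- Untreated diabetics: 3,000 × 0.10 × 0.10 = 30; 3,000 × 0.15 × 0.15 = 67.5; 3,000 × 0.20 × 0.25 = 150.
- Component e scored 0 despite the diagnosis: 30 × 0.25 = 7.5; 67.5 × 0.50 = 33.75; 150 × 1.00 = 150.
- Syndrome label wrong: 7.5 × 0.30 = 2.25; 33.75 × 0.40 = 13.5; 150 × 0.50 = 75.

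A second set of assumed rates (diabetes 5–15%, untreated 10–30%, glucose missing 10–50%) gives 3,000 × 0.05 × 0.10 × 0.10 = 1.5 to 3,000 × 0.15 × 0.30 × 0.50 = 67.5 patients with component e scored this way, and fewer with a changed label. Neither set includes patients with blank therapy status.

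**Step 5. Effect on the contrast**

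If a share s of the no-syndrome group really belongs to the syndrome group and resembles it on average, the observed difference is (1 − s) times the true one. Assume 1,000 to 2,000 patients in the no-syndrome group. Then 14 misplaced patients give s = 14/2,000 = 0.7% to 14/1,000 = 1.4%, and 75 give s = 75/2,000 = 3.75% to 75/1,000 = 7.5%.

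**The case against.** The strongest reply is that this follows from two broader features: fasting glucose is not a named data item, and missing components are set to 0. If glucose were collected and a missing component stayed missing, this patient would no longer be scored 0. Protocol 14.1 and 14.2 also provide for highlighting missing data and asking investigators to complete it. This is right about the cause, and it limits the size. But the recode to 0 is the SAP's current rule, and while it stands, any blank glucose value still produces the error.

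A second reply is that components b to e share one form, a measured value or treatment, and that the SAP says it follows a published definition. That publication cannot be checked from the documents, so no claim is made that the SAP departs from it. This reply stands for measured values. It does not cover the handling of blanks, which the SAP sets itself and already supplements for waist and lipids.

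Third, treatment for diabetes is not defined. If it included non-drug treatment, fewer patients would be affected.

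Three stronger readings are tempting and not supported:

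- A reader might infer that any recorded diabetes should meet component e, even with a measured glucose below 100 mg/dL. Nothing in the documents argues for overriding a measured value.
- A reader might infer that SAP 3.1 would produce contradictory tables. Its groupings include the syndrome as yes or no, but none is by glucose component, and being diabetic without meeting three criteria is no contradiction.
- A reader might infer that known diabetics in general land in the comparison group. The label changes only with no recorded treatment, a blank glucose value and exactly two other components, all at once.

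**Conclusion.** The point holds as a gap in the missing-data handling of one component. Under the rules as written, a diabetic recorded as untreated, or with blank therapy status, who has no glucose value is scored as not meeting component e, and is labelled free of the syndrome when exactly two other components are met. The information needed to avoid this is already collected.

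The effect is small: about 2 to 75 of 3,000 labels, middle value near 14. The range rests wholly on assumed rates, and its top end needs glucose to be missing for every untreated diabetic. At the middle value the group difference would shrink by about 1%. The error goes only one way, so a larger registry would not average it out. This is a minor point, worth making because the remedy is nearly free and the variable feeds a main analysis.

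**What to change.** Add to component e in SAP 3.2 (Evaluation of the metabolic syndrome): *When fasting glucose is missing, a recorded diagnosis of diabetes (treated or untreated) will count as meeting this component.* State that this step runs before the recode to 0 in SAP 3.1. Because it relies on the diagnosis, it also covers patients whose therapy status is blank.

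This parallels the BMI fallback for missing waist and leaves the scoring of measured glucose values unchanged. The cost is one sentence and one extra program condition, with no new data. It does not resolve blank glucose in patients without a diabetes diagnosis, who would still be scored 0 under the general rule.
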